### **7.3 Adverse Events and Serious Adverse Events**

**AE Definition:** AE is any untoward or unfavorable medical occurrence in a human study participant, including any abnormal sign (e.g. abnormal physical exam or laboratory finding), symptom, or disease, temporally associated with the participants' involvement in the research, whether or not considered related to participation in the research.

**AEs for this study include:** There are no known expected or unexpected adverse events. Rather, discontinuing these medications lowers the risk of an adverse event from these medications.

**SAE Definition:** SAEs consist of any adverse event that results in death; is life threatening or places the participant at immediate risk of death from the event as it occurred; requires or prolongs hospitalization; causes persistent or significant disability or incapacity; results in congenital anomalies or birth defects; is another condition which investigators judge to represent significant hazards

**SAEs for this study include:** None

As there are no expected AEs or SAEs, we will not capture solicited AEs or SAEs. Unsolicited AEs and SAEs will be noted during clinical care. Once each month, clinician value champions will be asked to send all adverse event forms to the study coordinator. No SAEs are expected as described above. All deaths within the study cohort will also be reported along with a cause of death

### 7.3.1 Reporting Procedures

All data and safety monitoring reporting will classify SAEs and AEs as to their severity, as per the definitions below:

- **Mild:** Awareness of signs or symptoms, but easily tolerated and are of minor irritant type causing no loss of time from normal activities. Symptoms do not require therapy or a medical evaluation; signs and symptoms are transient.
- **Moderate:** Events introduce a low level of inconvenience or concern to the participant and may interfere with daily activities, but are usually improved by simple therapeutic measures; moderate experiences may cause some interference with functioning
- **Severe:** Events interrupt the participant's normal daily activities and generally require systemic drug therapy or other treatment; they are usually incapacitating.

All data and safety monitoring reporting will classify SAEs and AEs as to potential relatedness to the study intervention as per the definitions below:

- **Definitely Related:** The adverse event is clearly related to the investigational agent/procedure – i.e. an event that follows a reasonable temporal sequence from administration of the study intervention, follows a known or expected response pattern to the suspected intervention, that is confirmed by improvement on stopping and reappearance of the event on repeated exposure and that could not be reasonably explained by the known characteristics of the subject's clinical state.
- **Possibly Related:** An adverse event that follows a reasonable temporal sequence from administration of the study intervention follows a known or expected response pattern to the suspected intervention, but that could readily have been produced by a number of other factors.
- **Not Related:** The adverse event is clearly not related to the investigational agent/procedure - i.e. another cause of the event is most plausible; and/or a clinically plausible temporal sequence is inconsistent with the onset of the event and the study intervention and/or a causal relationship is considered biologically implausible.

### 7.3.2 Follow-up for Adverse Events

**Adverse event reporting schedule:** Once each month, clinician value champions will be asked to send all unexpected adverse event forms to the study coordinator. No SAEs are expected as described above. All deaths within the study cohort will also be reported along with a cause of death.

- All **adverse events that are both serious (SAE) and unexpected** (i.e., have not been previously reported for the study's intervention) will be reported to the IMPACT Collaboratory Regulatory and Data Team Leader ([name] PhD), Advarra IRB, NIA IMPACT Collaboratory PO ([name]), and the IMPACT Collaboratory DSMB Chair within 48 hours of the study's knowledge of SAE.
- The summary of all other SAEs will be reported to IMPACT Collaboratory Regulatory and Data Team Leader ([name] PhD), Advarra IRB, NIA IMPACT Collaboratory PO ([name]), and the IMPACT Collaboratory DSMB Chair quarterly, unless otherwise requested by the DSMB Chair.
- All deaths will be reported to IMPACT Collaboratory Regulatory and Data Team Leader ([name] PhD), Advarra IRB, NIA IMPACT Collaboratory PO ([name]), and the IMPACT Collaboratory DSMB Chair and to the DSMB Chair within 24 hours of study's knowledge of death.
- AEs will be reported per IRB policies and also to IMPACT Collaboratory Regulatory and Data Team Leader ([name] PhD), Advarra IRB, NIA IMPACT Collaboratory PO ([name]), and the IMPACT Collaboratory DSMB Chair and to the DSMB Chair at minimum every 6 months, or at a frequency requested by NIA and/or by the DSMB.

### 7.4 Safety Monitoring

The Principal Investigator (PI) will be responsible for ensuring participants' safety on a daily basis. In addition, the NIA IMPACT Collaboratory DSMB will oversee all data and safety monitoring activities for this study. The number of DSMB members will be determined by NIA, and one will be designated the Chairperson. DSMB members will be appointed by the NIA Director. This DSMB will act in an advisory capacity to the NIA Director to monitor participant safety, to evaluate the progress of the study, and to review procedures for maintaining the confidentiality of data, the quality of data collection, management, and analyses. Advarra IRB will conduct the ethical review required for the protection of human subjects. NIA PO, in consultation with DSMB chair, will make a determination regarding the level and format of data and safety monitoring this study requires.

## 8 INTERVENTION DISCONTINUATION

### Patient Subjects:

N/A – The goal of the value champion intervention, deprescribing of potentially inappropriate medications, is considered acceptable and standard clinical care at

intervention clinics. We will analyze secondary data of all eligible Medicare beneficiaries whether or not they reduce use of the targeted medications in response to the value champion interventions, and thus it is not possible for subjects to discontinue early. Reduction in use is likely to improve overall health, and we do not expect needed follow up for those who reduce their use of these medications.

Clinician Subjects:

Value Champions may end participation in the study for any reason. In that case, an alternative clinician Value Champion may be identified to replace the VC at that clinic if feasible considering the timing of withdrawal during the study period.

## **9 STATISTICAL CONSIDERATIONS**

### **9.1 General Design Issues**

Our hypothesis is that for each medication class, the intervention will produce clinically relevant decreases in mean possession rates of 10% of a standard deviation in patients seen in intervention clinics compared to those who are seen in control group clinics.

The study design was chosen to meet the requirements of the funder for a non-pharmacologic/non-device intervention for people living with dementia, conducted in a health system setting. The 24-months of funding is for a demonstration project, intended to demonstrate the feasibility and acceptability of the intervention, but with the stipulation by the funder that the trial must be a randomized controlled trial, one with a control group. In response, we proposed a cluster-randomized trial where the intervention will be randomized at the primary care clinic level, not the patient level, and existing health systems claims data will be used to address our primary outcome (Specific Aim #1) and one of our secondary outcomes: Specific Aim #2: emergency department visits and hospitalizations for a fall.

The primary outcome measure for this study will be medication possession rates (MPR) per quarter, for the 3 therapeutic classes of medications - antipsychotics, benzodiazepines, and hypoglycemics - that are considered low-value for beneficiaries with dementia. Unlike many studies using medication possession rates to exam adherence, we are interested in reducing, not increasing, the percent of days covered. Following an intent-to-treat design, claims data from all Medicare beneficiaries meeting our dementia eligibility criteria prior to the start of the value champion intervention will be included in the analysis. To determine the impact of the intervention, we will construct hierarchical models with time period observations nested within patient. These models will be random effects or generalized estimating equations (GEE) with robust standard errors, and will be either linear, if original MPRs are used as outcome, or generalized linear, if transformation necessary. The key variable of interest in these models will be the treatment indicator (assigned based on practice randomization to intervention or control group).

### **9.2 Sample Size and Randomization**

Our sampling plan anticipates enrolling at least 30 of the 39 practices in USMM and 26 of the 28 practices in Ochsner. Based on Medicare enrollments of 39,000 members in USMM with a 20 percent dementia rate in 2019, and 10,000 members in Ochsner with approximately 10 percent of members diagnosed with dementia in 2019, we should have

at least 2,000 patients per treatment group for USMM and 500 patients per treatment group for Ochsner. For our primary outcome, with a follow-up period of one year and with mediation possession rates calculated per patient each quarter, we will have approximately 4 MPR observations per patient or 8,000 observations per group for USMM analyses and 2,000 per group for Ochsner. Even after assuming significant correlation across time within patient and modest correlation between patients within a practice, which will reduce effective sample sizes by 20%, we should have the equivalent of 6,400 observations per treatment group for our USMM analyses and 1,600 observations per treatment group for Ochsner.

The expectation of our intervention is that for each medication class, it will produce clinically relevant decreases in mean possession rates of 10% of a standard deviation. If the effect size is this large for a medication class and using a 5% level of significance, our Ochsner sample (with effective size of at least 1,600 per group) will have 80% power to discern a significant difference, while our larger USMM sample (with effective size of at least 6,400 per group) will have almost 100% power. Indeed, our USMM sample will have 80% power to find a significant difference, even if the effect size is only 5% of a standard deviation

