## **4 SELECTION AND ENROLLMENT OF PARTICIPANTS**

### **4.1 Inclusion Criteria**

Clinician practices within two ACOs will be eligible for participation in the study if they meet the following criteria:

- a. They include 3 or more primary care providers (defined as a primary care physician (specialty code of 08 or 11), nurse practitioner (specialty code = 50) or physician's assistant (specialty code = 97)) and
- b. They have clinical encounters with 10 or more Medicare beneficiaries with Alzheimer's or Alzheimer's related dementia in the base years (2019-2020).

Medicare beneficiaries will be included in the study if they meet all of the following criteria during the intervention year:

- a. They are seen by a clinician at a participating practice as evidenced by one or more evaluation and management claim,
- b. They have continuous coverage in Medicare Parts A, B and D and no months of Part C (Medicare Advantage),
- c. They have two or more claims with an ICD-10 diagnosis for Alzheimer's or Alzheimer's related dementia 30 days apart or 1 inpatient stay with a principal diagnosis of Alzheimer's.

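### Ochsner's 500 patients per group uses every member with dementia implied by the plan's own inputs, so the 80% power stated for a minimum sample is not supported

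*Combined protocol and SAP*

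**What the plan says.** Section 9.2 derives both ACO samples in one sentence, from membership multiplied by a 2019 dementia rate. For USMM the inputs are "39,000 members in USMM with a 20 percent dementia rate in 2019"; for Ochsner they are "10,000 members in Ochsner with approximately 10 percent of members diagnosed with dementia in 2019". The result is given as "at least 2,000 patients per treatment group for USMM and 500 patients per treatment group for Ochsner".

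The same section expects to enrol "at least 30 of the 39 practices in USMM and 26 of the 28 practices in Ochsner". It counts "approximately 4 MPR observations per patient or 8,000 observations per group for USMM analyses and 2,000 per group for Ochsner", and then allows for correlation, "which will reduce effective sample sizes by 20" percent. That leaves 6,400 effective observations per group for USMM and 1,600 for Ochsner. The next paragraph describes 1,600 as the least the Ochsner effective size will be, and states 80% power for a 0.10 SD difference at the 5% level.

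Eligibility is set in sections 3, 4.1 and 4.2, identically for both ACOs:
- a visit claim at a participating practice;
- insurance coverage, worded as "They have continuous coverage in Medicare Parts A, B and D and no months of Part C (Medicare Advantage");
- two dementia claims 30 days apart, or one inpatient stay with Alzheimer's as the principal diagnosis;
- no metastatic cancer, and no hospice enrolment in the six months before the intervention starts.

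**The concern.** The two ACOs are treated differently without explanation. USMM's planned number is well below its stock of members with dementia, which leaves room for non-participating practices and ineligible patients. Ochsner's planned number equals its whole stock, which leaves none. Yet the Ochsner figure is carried forward as a minimum and supports a separate power statement for that ACO.

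What is at stake is how an Ochsner result would be read. If the ACO is analysed separately, as section 9.2 implies, a null finding would be judged against a stated 80% power whose input leaves no room for any loss of patients.

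**Working it through.** **1. Implied stock and planned yield (inputs from section 9.2)**

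Yield = planned patients ÷ (members × dementia rate).

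| ACO | Members × rate | With dementia | Planned | Yield |
|---|---|---|---|---|
| USMM | 39,000 × 20% | 7,800 | 2 × 2,000 = 4,000 | 51.3% |
| Ochsner | 10,000 × 10% | 1,000 | 2 × 500 = 1,000 | 100% |

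**2. Reproducing the stated power**

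Effective observations per group: 500 × 4 quarters × 0.8 = 1,600.

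Power = Φ(d√(n/2) − 1.96), with d = 0.10 and n = 1,600: 0.10 × √800 = 2.828; 2.828 − 1.96 = 0.868; Φ(0.868) = 80.7%.

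This matches the stated 80%. The plan does not say whether the test is one- or two-sided. A one-sided 5% test gives 88.2%, which does not match, so two-sided is taken as intended.

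**3. The break-even yield**

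Effective observations needed for 80% power: n = 2(1.96 + 0.842)² ÷ 0.10² ≈ 1,570 per group.

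In patients: 1,570 ÷ (4 × 0.8) ≈ 491 per group, or about 981 in total.

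Break-even yield: 1,570 ÷ 1,600 = 98.1%. Losing about 19 of the 1,000 members uses up the margin.

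**4. Sensitivity to the unknown yield**

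The true Ochsner yield is not in the documents, so the yields below are assumptions. Patients per group = 500 × yield, and effective observations = patients × 4 × 0.8. Power is as in step 2, with the plan's 20% reduction unchanged.

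| Assumed yield | Patients per group | Effective per group | Power |
|---|---|---|---|
| 100% (plan) | 500 | 1,600 | 80.7% |
| 90% | 450 | 1,440 | 76.5% |
| 80% | 400 | 1,280 | 71.6% |
| 70% | 350 | 1,120 | 65.8% |
| 60% | 300 | 960 | 59.1% |
| 51.3% (USMM's planned minimum) | 256 | 821 | 52.6% |

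**The case against.** **The missing practices may be small.** Taking 26/28 of the patients would give 464 per group and 77.8% power, but that assumes practices of equal size. Section 4.1 drops practices with fewer than 10 dementia beneficiaries. If both absent practices fail that rule, they hold at most 2 × 9 = 18 patients. That leaves 982 ÷ 2 = 491 per group, 491 × 3.2 = 1,571 effective observations, and 80.0% power. This stands: 464 is not a supported figure. But even this favourable case uses all the slack before any patient is lost to coverage, visit, claims-pattern, cancer or hospice criteria. If the practices drop out for another reason, the loss is unknown.

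**USMM's 51% is not an eligibility rate.** It is a stated minimum, and its base includes practices that will not enrol. Within 30 of 39 practices of equal size the base is 7,800 × 30/39 = 6,000, and the yield is 4,000 ÷ 6,000 = 66.7%. This also stands. Carrying 51% over to Ochsner is a sensitivity value, not a forecast.

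**The 1,000 may not be a ceiling.** It is an approximate 2019 count. Sections 3, 4.1 and 6.2.1 assess eligibility during the intervention year (the Précis and section 9.1 place it before the start), so later diagnoses could enter. Section 3 uses a dementia definition broader than the CMS one, and the documents do not say which definition produced the 10%, or whether that count was already filtered for coverage. All of this is possible, but the plan claims none of it. Reaching 981 eligible patients would take 981 ÷ 0.9 = 1,090 members with dementia (10.9%) at a 90% yield, or 981 ÷ 0.8 = 1,226 (12.3%) at 80%.

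**The stated power is correct arithmetic, and conduct would not change.** Both are true. All eligible beneficiaries are analysed from claims whatever the forecast. The point is an unsupported input, not a miscalculation.

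**Conclusion.** On the plan's stated inputs, 500 Ochsner patients per group is the full stock of members with dementia, and calling 1,600 effective observations a minimum is not supported. The 80% power survives only if at least about 98% of those members qualify. The direction is clear unless the 1,000 was already filtered or has since grown. The size of the shortfall is not known. All powers here are conditional on the flat 20% correlation reduction, whose adequacy is a separate question, so they come before any correction for clustering.

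Four stronger readings may be tempting, and the documents do not support them:
- **That the eligibility rules cannot deliver 500 per group.** The count is approximate, dates from 2019, and has no stated definition.
- **That Ochsner should be expected to have 256 to 464 patients per group and 53% to 78% power.** The lower end borrows a minimum from another ACO, and the upper end assumes equal practice sizes.
- **That the study total falls to about 4,500 to 4,900.** This holds USMM at its minimum of 4,000, although USMM could exceed it and offset a loss at Ochsner. The Précis says only approximately 5,000.
- **That the pooled two-ACO analysis is the adequately powered one.** Section 9.2 gives power by ACO only, and no pooled calculation exists.

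**What to change.** In section 9.2:

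1. Remove the *at least* wording from the Ochsner sample and effective size.
2. Replace 500 per group with the expected eligible Ochsner count after practice selection and every filter in sections 3, 4.1 and 4.2. State the data year and the dementia definition behind it. The claims screening that section 6.2.1 schedules for months 1 to 3 can supply this. Because eligibility may be finalised later, label the count as a projection.
3. Restate the Ochsner power from that count. Until it is available, show power over a range of assumed yields, marked as sensitivity values before any correction for clustering: about 77% at 90%, 72% at 80%, 66% at 70%, 59% at 60%, and 53% at 51%.
4. State whether the per-ACO or a pooled comparison is primary. Do not claim power for a pooled analysis until it has been calculated.

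The cost is a query on data already held and revised text. No extra patients are needed. The downside is a less favourable stated power for Ochsner.

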#### Screening

##### Patient Subjects:

Screening of eligible participants will be done by the programmer/analyst at IAC by applying study inclusion / exclusion criteria as described above in Section 4.1. This screening and selection will take place months 1-3 of the study prior to the value champion intervention. All Medicare beneficiaries at eligible ACOs will be included if they

meet eligibility criteria during the intervention year.

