### **7.2 Methods and Timing for Assessing, Recording, and Analyzing Safety Parameters**

As data used to measure the primary outcome is de-identified, contains no PHI, and is collected after the intervention is completed. However, to ensure that we capture any unexpected AEs, we will ask each clinician champion to monitor for any unexpected adverse events and complete an adverse event form if they see one. Once each month, clinician value champions will be asked to send all adverse event forms to the study coordinator. No SAEs are expected as described above. All deaths within the study cohort will also be reported along with a cause of death

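### The Ochsner sample size makes no allowance for death or loss of coverage, and its stated 80% power has only 1.9% slack

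*Combined protocol and SAP*

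**What the plan says.** Section 9.2 expects at least 2,000 patients per group at USMM and 500 at Ochsner. It then says that "we will have approximately 4 MPR observations per patient or 8,000 observations per group for USMM analyses and 2,000 per group for Ochsner". Section 3 (Duration of Enrollment and Follow-up) repeats these counts. One reduction follows, attributed to correlation over time within a patient and between patients within a practice, "which will reduce effective sample sizes by 20" per cent. That leaves 6,400 and 1,600 effective observations per group.

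The power statements rest on those two figures: "our Ochsner sample (with effective size of at least 1,600 per group) will have 80% power to discern a significant difference", and "our larger USMM sample (with effective size of at least 6,400 per group) will have almost 100% power", both at an effect of 0.10 SD. A further sentence gives USMM 80% power at 0.05 SD.

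On timing, section 6.2.1 (Screening, Patient Subjects) says "This screening and selection will take place months 1-3 of the study prior to the value champion intervention". The intervention description in section 2 puts training in months 4-9, and section 3 puts follow-up in the year after training. On deaths, section 7.2 says "All deaths within the study cohort will also be reported along with a cause of death".

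**The concern.** The calculation credits every patient with all four outcome quarters. The cohort consists of people with dementia aged 65 and over. Some will die, lose Part D or move to Part C before the last outcome quarter, and each such patient supplies fewer than four MPRs, possibly none. The 20% reduction cannot be read as covering this, because the text assigns it wholly to correlation.

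The omission matters if the stated power has little margin. Power is claimed for each ACO separately, so a null result at Ochsner would be read against an 80% figure whose inputs assume that nobody dies or leaves.

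**Working it through.** **Inputs from the plan.** 500 and 2,000 patients per group, four quarters, 20% reduction, effects of 0.10 and 0.05 SD, 5% significance (all section 9.2), 1:1 allocation (section 4.3). Sidedness is not stated. Two-sided reproduces the plan, while one-sided gives 88.2% and does not.

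**Plan's own figures.** 500 x 4 x 0.8 = 1,600 and 2,000 x 4 x 0.8 = 6,400. With power = Φ(d√(n/2) − 1.96):

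- Ochsner, d = 0.10, n = 1,600: Φ(2.828 − 1.96) = 80.7%
- USMM, d = 0.05, n = 6,400: 80.7%
- USMM, d = 0.10, n = 6,400: 99.99%

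The stated powers are reproduced.

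**Slack.** n for 80% power = 2(1.96 + 0.8416)²/d² = 1,570 at 0.10 SD and 6,280 at 0.05 SD. So 1 − 1,570/1,600 = 1 − 6,280/6,400 = 1.9%.

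**Is there a reserve of patients?**

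- Ochsner: 10,000 x 10% / 2 = 500 per group, the whole stated source before any coverage criterion is applied. Scaled to 26 of 28 practices (assuming equal practice size) it is 464 per group, or 1,486 effective observations and 77.8% power before any loss.
- USMM: 39,000 x 20% / 2 = 3,900 per group, or 3,000 scaled to 30 of 39 practices on the same assumption. That gives 12,480 or 9,600 effective observations and 97.7% or 93.4% power at 0.05 SD. Between 50% and 35% could be lost before power fell below 80%.

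**Size of the effect at Ochsner.** The documents give no loss rate, so 10-25% a year from all causes is assumed, at a constant hazard. The probability of being observed at time t is (1 − a)^t, with t in years and a the annual loss, taken at quarter mid-points. Two start times are used:

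- Cohort fixed before training, outcomes 6-18 months later: t = 0.625, 0.875, 1.125, 1.375.
- Loss starting with the outcome year: t = 0.125, 0.375, 0.625, 0.875.

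Two ways of costing a lost quarter are used:

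- Proportional: 1,600 is multiplied by the mean fraction of quarters observed.
- Correlated: a patient with k quarters carries k/(1 + (k − 1)ρ) units of information, with ρ = 0.7 assumed. Three quarters of four keep 1.25/1.29 = 97%, while a patient with none loses everything. 1,600 is multiplied by the mean fraction of information kept.

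Example, 10% a year with the cohort fixed before training: the four fractions are 0.936, 0.912, 0.888 and 0.865, mean 0.900. Effective n is about 1,441, and power is Φ(0.10 x √720.5 − 1.96) = 76.5%. With ρ = 0.7 the information kept is 0.928, effective n is about 1,485 and power is 77.8%.

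| Annual loss (assumed) | Before training, ρ = 0.7 | Before training, proportional | Outcome year only, ρ = 0.7 | Outcome year only, proportional |
|---|---|---|---|---|
| 10% | 77.8% | 76.5% | 79.9% | 78.7% |
| 15% | 76.1% | 74.2% | 79.4% | 77.6% |
| 25% | 72.4% | 68.9% | 78.4% | 75.1% |

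At 5% a year with the cohort fixed before training, power is 79.3% (ρ = 0.7) or 78.7% (proportional).

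Both costings are shown because the plan does not state ρ. It calls the correlation over time significant, which favours the milder columns. Yet if its whole 20% were within-patient correlation, 1/(1 + 3ρ) = 0.8 gives ρ = 0.083, and costing is then close to proportional. The 20% itself is taken as stated here.

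**The case against.** Four points on the other side have force.

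1. **USMM.** A reader might infer that any loss above 1.9% breaks both 80% statements. The documents do not support that. USMM's 2,000 is given as a minimum, against 3,000-3,900 implied by the same paragraph. The plan does not say what the gap is for, but it may already cover loss. At the hypothesised 0.10 SD, USMM power stays at 99.9% even after a 20% proportional loss.

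2. **Timing.** A reader might take it as settled that outcomes end about 18 months after selection. That follows from selection in months 1-3, but the documents conflict. The Précis (Sample Size and Population) and section 9.1 set eligibility before the intervention. Section 3 (Study Population), section 4.1 and the last sentence of the patient screening text in 6.2.1 set it during the intervention year. If continuous coverage is required through that year, included patients would have nearly all four quarters. The loss would then appear as fewer than 500 patients per group rather than fewer quarters.

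3. **Repeated measures.** A fall to between 77% and 69% is the least favourable combination: earliest cohort and proportional costing. Correlated quarters soften it, as the table shows.

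4. **Small drop, assumed rate.** A 5% loss of effective observations still leaves 78.7%. The plan says approximately four observations, calls itself a demonstration project, and excludes metastatic cancer and recent hospice enrolment, which should lower early mortality.

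Points 1 to 3 limit the claim and are accepted. Point 4 limits its consequence. None supplies the missing allowance: the word approximately is never turned into a deduction, and the exclusions also reduce the 500.

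**Conclusion.** The concern holds for Ochsner. Section 9.2 states no allowance for loss, the 500 per group leaves no reserve, and the stated 80% power at 0.10 SD has 1.9% slack. These statements need no assumption beyond a two-sided test.

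The size of the shortfall does rest on assumptions. With 10-25% annual loss and ρ = 0.7, power is about 78% to 72% if the cohort is fixed before training and about 80% to 78% if loss starts with the outcome year. Proportional costing gives 77% to 69% and 79% to 75%. The smallest effect detectable with 80% power, 0.10 x √(1,570/1,600) = 0.099 SD as planned, would rise to 0.103-0.110 SD in the first case with ρ = 0.7, from effective sizes of about 1,485 and 1,306 (1,600 x 0.928 and 1,600 x 0.816).

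For USMM, the 0.05 SD statement has the same 1.9% slack on its printed 6,400, but a real shortfall is not shown. This is an overstatement of precision at one ACO. It does not invalidate the design.

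**What to change.** 1. Reconcile the eligibility window: the Précis and section 9.1 against sections 3, 4.1 and 6.2.1.
2. Apply the reconciled rule to the 2019-2020 claims that the plan already uses to select clinics. Count the eligible Ochsner patients and the quarters each contributes over the matching outcome period. If the cohort is fixed before training, an 18-month span fits within those 24 months provided that eligibility is established in the first six.
3. In section 9.2, and in section 3 where the counts are repeated, replace the Ochsner figures of four observations per patient, 2,000 and 1,600, and the 80% power, with values net of that loss. Alternatively, restate the smallest effect detectable with 80% power.
4. For USMM, state whether the minimum of 2,000 per group already covers loss. If it does not, make the same adjustment to the 0.05 SD statement.

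The cost is one count and some revised wording, with a slightly less favourable stated power at Ochsner. No patients are added, and the planned models do not change.
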